01.12.2024

Comparative Evaluation of the Possible Effects of Platelet Rich Plasma (Prp) and Low Level Laser (Biolase) on Postoperative Complications and Wound Healing After Extraction of Impacted Wisdom Teeth

Study Protocol

The study was conducted on a total of 30 patients aged between 18 and 40 years who applied to the XXX Oral and Maxillofacial Surgery Department Clinic for bilateral, similar position, half mucosa and bone retention lower impacted wisdom teeth extraction. First, clinical and radiological evaluations were performed on the patients. In the clinical evaluation, systemic status, tooth deficiency, occlusion and the status of the impacted tooth were evaluated. Panoramic film was taken for radiographic evaluation.

Inclusion criteria;

- Individuals aged 18 years and over,
- Patients with partially impacted wisdom teeth,
- Individuals with systemic status according to ASA classification as ASA0 and ASA1,
- Individuals who have not used any medication in the last two weeks,
- Individuals who do not have a missing lower second molar.

Exclusion criteria for the study;

- Individuals with mouth opening less than 25 mm for various reasons,
- Pregnant and breastfeeding individuals,
- Individuals who do not come to postoperative check-ups,
- Individuals using different medications other than the recommended medication.

Individuals who were allergic to the study drugs and the materials to be used were excluded from the study. All patients were included in the study after detailed information about the study was provided and a consent form was signed by the patient. The study was initiated after permission was obtained from the XXX University Ethics Committee. (Decision No:) All operations were performed by the same physician in the operating room of the XXX University Faculty of Dentistry, Department of Oral and Maxillofacial Surgery, adhering to surgical principles and sterilization rules, under equal operating conditions.

Study groups; Randomized, prospective, split mouth and single core, 30 patients in total were divided into two groups.

Study groups were determined as follows:

- A. Platelet-rich plasma (PRP) applied group.
- B. Low-level laser therapy (LLLT) applied group.

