First group (one side of the same patients): Platelet-rich plasma (PRP, initially 1200 revolutions per minute (rpm), 10 minutes later 2000 rpm for 10 minutes); second group (other side of the same patient): low-level laser treatment, diode laser (Ezlase 940; Biolase Technology, Inc., Irvine, CA) 100 mW (0.1 W) was applied for a total of 120 seconds. After the surgery, these two groups (methods) were applied to the extraction socket at different times (with a 2-week interval between each surgery). Both surgical sites were sutured with 3/0 silk suture (18 mm, 3\8 sharp, 75 cm black, Dağsan Silk Suture). It was randomly determined which material would be used first on which side. The other side was operated on after 2 weeks. Using an automatic centrifuge machine, PRP was initially prepared at 1200 rpm for 10 minutes and then 3 layers were created. 1) An upper straw-colored PPP (platelet-poor plasma). 2) A middle cloudy layer rich in platelets. 3) A lower layer rich in red blood cells. The straw-colored upper layer was collected together with the cloudy layer and centrifuged again at 2000 rpm for 10 minutes. Leukocyte-rich PRP was formed at the bottom of the test tube; the upper PPP was discarded using a pipette. 1 ml (10%) calcium chloride was added to the Platelet Rich Plasma for activation. (50 microliters of 10% calcium chloride is added for 1.0 mL of PRP). Gel was formed after 10 minutes. This layer consisting of approximately 2 ml of PRP was then placed in the extraction socket within 2 minutes after surgical removal of the mandibular third molar. The second group received a single session of intraoral 940 nm diode laser (BIOLASE) for 120 seconds immediately after suturing.

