The patients were checked in the first session they came to, and on the 2nd and 7th days after the operation. After the operation in all patients; Amoxicillin 1000mg (Largopen 1000mg,2*1 (Bilim Ilac Sanayii Ve Ticaret A.S. Istanbul, Turkey), Dexketoprofen 25mg (Arveles 25mg, 2*1 (Menarini, Istanbul, Turkey)), benzylamine HCl + chlorhexidine gluconate gargle (Andorex 200ml gargle, 3*1 (Humanis Sağlık A.S. Istanbul, Turkey) were used routinely. Sutures were removed after 1 week. Pain was assessed with Visual Analog Scale (VAS) at 3, 6, 9, 12 and 24 hours and on days 2, 3, 4, 5, 6 and 7. Angulus-tragus, angulus-lateral canthus, angulus-nasalis, angulus-labial commissure and angulus-pogonion points were used to evaluate edema. Measurements were made immediately before, 2 days after and 7 days after the operation. For the evaluation of trismus, mouth opening - the distance between the incisal edges of the central teeth during maximum mouth opening - was measured immediately before, 2 days after and 7 days after the operation. As a result, statistical analysis was performed and interpreted for the

obtained data. Before surgical extraction of the impacted tooth, the inferior alveolaris and buccal nerve were local anesthetized and the buccal flap was elevated mucoperiosteally with a 'Winter' incision using a scalpel number 15. A 1.6 mm diameter steel carbide round cutter, fissure cutter burs, a surgical micromotor operating at 1400 rpm and serum irrigation were used to remove the bone. The teeth were exposed. The teeth were then divided into two by bur and extracted with the help of a dental elevator. During the operation, 2 ampoules of local anesthetic (Ultracain 69 DS forte-Aventis İlaç Sanayi Tic. A1, Turkey) containing 40 mg/ml articaine HCl and 0.012 mg/ml epinephrine HCl were used as local anesthetic solution in all groups. The flap was closed primarily with 3/0, 19 mm atraumatic silk sutures and 3/8 round needles. The time between the first incision and the last suture was calculated and recorded.

Statistical Analysis Plan

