All statistical analyses were performed in a statistical software program (SPSS version 26.0, IBM Corp.). Mean, standard deviation, median, minimum and maximum values were calculated for descriptive statistics. Categorical data were shown with frequency and percentage. The conformity of the data to normal distribution was evaluated by examining the Shapiro-Wilk test and histograms. Comparisons between the two treatment groups were made with the Student-T test for data suitable for normal distribution, while the Mann-Whitney U test was used for data not suitable for normal distribution. In order to find statistical differences in the time-dependent changes in the measured data in both treatment groups, repeated measures ANOVA test was used for normally distributed data and Bonferroni test was used for post-hoc comparisons. Friedman test was applied to non-normally distributed data and Dunn-Bonferroni test was used for post-hoc comparisons. Chi-square test was applied for comparison of categorical data. Significance level was determined as $p<0.05$.

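### Mouth opening is shared by both sides, so the trismus comparison is a two-week crossover with no check for carry-over or order

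*Combined protocol and SAP*

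**What the plan says.** The Study Protocol describes the design as "Randomized, prospective, split mouth and single core, 30 patients in total were divided into two groups", with PRP on one side and laser on the other side of the same patient. The two operations are done "with a 2-week interval between each surgery". The protocol adds that "The other side was operated on after 2 weeks" and attaches no condition on recovery of mouth opening. On order it says only that "It was randomly determined which material would be used first on which side". It mentions no blocking and gives no count of patients in each order.

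Trismus is "the distance between the incisal edges of the central teeth during maximum mouth opening", and it "was measured immediately before, 2 days after and 7 days after the operation".

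The Statistical Analysis Plan states: "Comparisons between the two treatment groups were made with the Student-T test for data suitable for normal distribution", with Mann-Whitney U as the non-normal alternative. Change over time within each treatment is tested by repeated measures ANOVA or Friedman. The plan names no period, order or carry-over term and no comparison of the two preoperative values. It does not say whether the treatments are compared on raw opening or on change from baseline.

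**The concern.** A split-mouth design works when each side carries its own outcome. Inter-incisal distance does not: both operations act on the same measurement. The last scheduled value after the first surgery is day 7, and the second surgery follows at about day 14. The opening recorded just before it therefore does two jobs. It is the baseline for the second treatment and a late result of the first.

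If opening has not fully recovered by then, part of the first treatment's effect is counted within the second treatment's results. A reader of the planned analysis could not separate a treatment difference in trismus from leftover restriction, although the second preoperative measurement could show whether there was any.

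**Working it through.** The documents give no sample-size calculation, SD or recovery data, so there is no planned figure to reproduce. The residuals, order splits and correlations below are assumptions used to show a range.

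**Timeline (days after surgery 1).** Preoperative 0, then 2 and 7; surgery 2 and its preoperative value at about 14; its day 2 and day 7 values at about 16 and 21. Nothing is scheduled between days 7 and 14.

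**Notation.** cP and cL are the mean losses of opening (mm) still present at surgery 2 after PRP first and laser first. nP and nL are the patients in each order, with nP + nL = 30. s is the fraction of the residual that persists into the second surgery's day 2 and day 7 values (0 to 1). A positive bias favours PRP.

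**Raw values.** Laser values are lowered by s·cP in nP patients, and PRP values by s·cL in nL patients:

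bias = s(nP·cP − nL·cL)/30

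With s = 1:
- 15:15, both residuals 2 mm: (30 − 30)/30 = 0.
- 15:15, cP = 1 and cL = 3: (15 − 45)/30 = −1.0 mm, half the 2 mm difference.
- 15:15, cP = 0 and cL = 4: −60/30 = −2.0 mm.
- 18:12, equal residual r: 6r/30 = 0.2r, which is 0.4 mm for r = 2 and 1.0 mm for r = 5.
- 20:10, equal residual r: 10r/30 = 0.33r, which is 0.67 mm for r = 2 and 1.67 mm for r = 5.

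Under simple randomisation of 30 patients, a split of 18:12 or worse in either direction has probability 0.36, and 20:10 or worse 0.099.

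**Change from each surgery's own preoperative value.** The second-period change is shifted by +(1 − s) times the residual. At 15:15:

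bias = (1 − s)(cL − cP)/2

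For cP = 1 and cL = 3:

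| s | raw values | changes |
|---|---|---|
| 1 | −1.0 mm | 0 |
| 0.5 | −0.5 mm | +0.5 mm |
| 0 | 0 | +1.0 mm |

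The two analyses err in opposite directions, so the choice the plan leaves open matters.

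**What a period term does (raw values, s = 1).** Let d be the true PRP-laser difference. The mean within-patient difference is d + cP for PRP-first patients and d − cL for laser-first patients. Averaging the two orders gives d + (cP − cL)/2. Equal residuals cancel whatever the split; unequal residuals do not.

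**What a carry-over check can detect (normal approximation, two-sided 0.05).** A paired check of second against first preoperative opening in 30 patients has 80% power at (1.96 + 0.84)/√30 = 0.51 SD of the paired difference. A comparison between orders, 15 v 15, needs (1.96 + 0.84)·√(2/15) = 1.02 SD for 80% power and has about 28% power at 0.5 SD.

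**Precision of first surgeries alone.** With SD σ and within-patient correlation ρ, the first-surgery standard error is σ√(2/15) and the paired one is σ√(2(1 − ρ)/30). The ratio is √(2/(1 − ρ)): 2.0 at ρ = 0.5 and 2.6 at ρ = 0.7.

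**The case against.** The strongest reply is that no carry-over has been shown. Two weeks may be enough for recovery, order was randomised, and equal residuals cancel exactly at 15:15. The millimetre figures with s = 1 are an upper end, because they carry the whole day-14 residual undiminished to days 16 and 21. A 20:10 split is uncommon. Trismus is one of several outcomes and none is named as primary. All of this stands, and it limits the point to a reporting and modelling request. It does not answer the case of unequal residuals, which random order does not remove and which is plausible in a trial asking whether two treatments differ in recovery.

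Three stronger readings are tempting, and the documents do not support them.
- A reader might infer that carry-over always pulls the comparison toward no difference. On raw values that happens only when the treatment with more residual also has the greater early loss, and the bias does not overshoot. With no early difference, unequal residuals create one; with opposite signs they widen it. Changes from baseline reverse the sign.
- A reader might infer that the exclusion "Individuals with mouth opening less than 25 mm for various reasons" removes patients at the second surgery because of the first treatment. The exclusion list does include events after enrolment, but nothing says this limit is applied again.
- A reader might conclude that incomplete recovery should confine the trismus result to first surgeries. Equal incomplete recovery does not bias a balanced comparison. Such a rule would at least double the standard error for ρ of 0.5 or more, and a low-powered check would be deciding the analysis.

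**Conclusion.** The point holds as a gap in the analysis plan; it does not establish bias. Mouth opening is one value per patient, both treatments act on it two weeks apart with no recovery condition, and the plan neither checks for carry-over nor allows for order.

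If restriction remains at the second surgery, the raw PRP-laser difference is biased by up to half the difference in residuals with balanced order. Equal residuals matter only with uneven order (0.2r at 18:12) and only if period is left out of the analysis. The direction depends on which treatment leaves more residual and on whether raw values or changes are analysed.

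These sizes rest on assumed residuals, additive effects and a preoperative value recorded at both surgeries. The protocol could also be read as a single baseline before the first surgery. The same risk would then remain but could not be seen in the data, and the report should say so. The point concerns trismus only, and the correction is cheap enough to be worth making.

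**What to change.** In the Statistical Analysis Plan, for trismus:

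1. Report surgery-2 minus surgery-1 preoperative mouth opening per patient, by which treatment came first, with estimates and confidence intervals. Give the number of patients in each order.
2. Make the PRP-laser comparison within patient with a period (order) term. State whether raw values or changes from baseline are used, and which baseline.
3. Always show the first-surgery-only PRP-laser comparison beside it as a sensitivity analysis. Qualify the trismus conclusion if the two disagree or if opening had clearly not recovered.

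Do not let a carry-over test or a judgement about recovery choose the primary analysis; a non-significant result at this size would not exclude carry-over. The document is written in the past tense, so if the data have already been examined, label these analyses as added afterwards.

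The cost is some SAP wording and two small tables, with no new data if both preoperative values were recorded. The first-surgery comparison is between patients (15 v 15 if balanced), so its wide interval should be read as a check on consistency.

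### The SAP plans no PRP-minus-laser difference with a confidence interval, so a non-significant result could not separate 'no important difference' from 'too imprecise to tell'

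*Combined protocol and SAP*

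**What the plan says.** The Statistical Analysis Plan is a single paragraph. For continuous data, "Mean, standard deviation, median, minimum and maximum values were calculated for descriptive statistics"; for the rest, "Categorical data were shown with frequency and percentage". The between-treatment step is a test: "Comparisons between the two treatment groups were made with the Student-T test for data suitable for normal distribution", with Mann-Whitney U as the non-normal alternative. Change over time is tested by repeated measures ANOVA or Friedman, with post-hoc comparisons. For categorical outcomes, "Chi-square test was applied for comparison of categorical data". The paragraph closes with "Significance level was determined as" p<0.05.

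The Study Protocol describes the design as "Randomized, prospective, split mouth and single core, 30 patients in total were divided into two groups". The two groups are PRP and low-level laser, one on each side of the same patient. No untreated or sham group is listed.

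Neither part mentions an estimated treatment difference, a confidence interval, an effect size, an important difference, an equivalence or non-inferiority margin, or a power calculation.

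**The concern.** The title promises a comparative evaluation of two active treatments. The natural answer is how much they differ and how precisely that is known. The planned outputs are summaries and test verdicts, and no listed output measures the precision of the comparison.

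This matters most if a comparison is not significant. There is no control group against which to place such a result, and 30 patients are given without any difference the trial was sized to detect. A p-value of 0.05 or more fits two quite different situations: the treatments differ by little, or the data are too few to say. Only an interval tells them apart. Without one, and without a rule on how to word a null result, a misreading as equal effectiveness is foreseeable.

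**Working it through.** The plan states no sample-size, power or precision figure, so there is nothing to reproduce. The question is what a reader could recover from the planned outputs, and how wide the missing interval would be.

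**Inputs from the documents:** 30 patients, split mouth, so 30 pairs if all are complete; significance level 0.05.

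**Assumptions, because the documents are silent:** two-sided testing; complete pairs; equal SD for the two treatments; within-patient correlation ρ between 0 and 0.7; results in SD units, because no SD is given.

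**1. Point difference.** With complete pairs, the mean of the within-patient differences equals the difference of the two means. If the descriptive statistics are given per treatment, the point difference follows by subtraction.

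**2. Paired interval.** Half-width = t(0.975, 29) × SD of differences / √30 = 2.045 / 5.477 = 0.37 SD of the paired differences. In SDs of a single measurement, the SD of differences is √(2(1−ρ)), so ρ is needed. It is not a planned output, and neither is the SD of differences.

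**3. Results over the assumed range.** Power comes from the noncentral t distribution with 29 df and noncentrality d√30 / √(2(1−ρ)). All figures are in SDs of a single measurement. The paired rows assume a paired t-test, which the SAP does not name.

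| Analysis | √(2(1−ρ)) | 95% half-width | Difference detectable at 80% power | Power at a true 0.5 SD |
|---|---|---|---|---|
| Paired, ρ = 0 | 1.414 | 0.53 | 0.75 | 47% |
| Paired, ρ = 0.3 | 1.183 | 0.44 | 0.63 | 61% |
| Paired, ρ = 0.5 | 1.000 | 0.37 | 0.53 | 75% |
| Paired, ρ = 0.7 | 0.775 | 0.29 | 0.41 | 93% |
| Unpaired t as named, 30 sides per arm | – | 0.52 | 0.74 | 48% |

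**4. What a null result would leave open.** With an observed difference of zero, the paired interval runs to 0.37 SD of the paired differences in each direction. If the result only just misses significance, its far limit is about 2 × 0.373 = 0.75 SD. That second case is the extreme. A bare p≥0.05 does not show which case applies.

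**5. What a reader could rebuild.** Means, SDs and n give only the unpaired interval, with half-width 0.52 SD whatever the correlation. At ρ = 0.5 that is 0.517 / 0.373 = 1.4 times the paired width; at ρ = 0.7 it is 0.517 / 0.289 = 1.8 times.

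**The case against.** The strongest reply is that much of the information is already there. The point difference follows by subtraction, so a significant result does carry a size. An unpaired interval can also be rebuilt, and it is conservative when the within-patient correlation is clearly positive. This stands. A reader might infer that the results would be uninterpretable, or would have no effect size at all, and the documents do not support that. What is lost is the paired interval.

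A reader might also infer that non-significance is the likely outcome. That is not shown. The documents give no effect, SD or correlation, and the paired power at a true 0.5 SD difference runs from 47% to 93% over the assumed correlations. The power figures in the paired rows also belong to a test the SAP does not name.

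A third tempting reading is that the plan sets out to call the treatments equally effective. Nothing in the documents claims or plans equivalence, similarity or non-inferiority. The misreading is a foreseeable risk, not a stated intention.

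It can be said that the statistical software prints an interval with the t-test anyway. Printed output is not a commitment to report, and for the unpaired tests named in the SAP that interval would ignore the pairing.

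Finally, the unpaired tests and the missing sample-size rationale are separate problems, and part of the force here comes from them. The point still stands by itself: changing to a paired test would, without more, still yield only a p-value. The overlap does constrain the remedy. A paired interval beside an unpaired p-value can contradict it. At ρ = 0.5, an observed difference between 0.37 and 0.52 SD gives a paired interval excluding zero and an unpaired p above 0.05.

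**Conclusion.** The omission is real, and nothing suggests it comes from redaction or text extraction. If the SAP is followed as written, the comparison of PRP with laser has a recoverable point difference but no recoverable paired measure of precision. A non-significant result therefore cannot be sorted into no important difference or too imprecise to tell. The missing interval would not be negligible: 0.37 SD of the paired differences either side, or 0.53 to 0.29 SD of a single measurement. These sizes rest on 30 complete pairs, a paired analysis and assumed correlations of 0 to 0.7. They illustrate scale and do not predict the result. This is a reporting defect that should be corrected; the data remain usable.

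**What to change.** For each outcome and time point, report the within-patient PRP-minus-laser difference with its 95% confidence interval from a paired analysis:

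- the paired mean difference where means are analysed, with the paired t-test;
- the Hodges-Lehmann estimate where ranks are used, with the Wilcoxon signed-rank test;
- the paired difference in proportions for categorical outcomes, with a McNemar-type test.

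Take each p-value from the matching paired test, in place of the unpaired tests now named, so that interval and test agree.

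Add a sentence that p≥0.05 is reported as no difference shown, and not as similarity or equivalence. Make no equivalence claim unless a margin was fixed before analysis. The text is in the past tense, so that moment may have gone; in that case report the estimates and intervals and stop there.

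**Cost.** No new patients, visits or measurements; re-analysis of existing data is enough. The continuous outcomes give about 23 postoperative intervals: 11 pain times, 5 edema lines × 2 visits = 10, and mouth opening at 2 visits. Null results will be stated more cautiously.

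### No paired comparison is named for a split-mouth trial, and a normality check with no stated unit chooses the tests

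*Combined protocol and SAP*

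**What the plan says.** The Study Protocol section describes a split-mouth trial in 30 patients. PRP goes on one side, and laser is the "second group (other side of the same patient"). The two operations are two weeks apart, with the order and side of the treatments set at random. Pain is recorded by "Visual Analog Scale (VAS) at 3, 6, 9, 12 and 24 hours and on days 2, 3, 4, 5, 6 and 7", which is 5 + 6 = 11 times per treatment. Edema and mouth opening are measured before surgery and on days 2 and 7.

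The Statistical Analysis Plan section first states: "The conformity of the data to normal distribution was evaluated by examining the Shapiro-Wilk test and histograms". Its rule for the treatment comparison is: "Comparisons between the two treatment groups were made with the Student-T test for data suitable for normal distribution". Otherwise, "the Mann-Whitney U test was used for data not suitable for normal distribution". For change over time, "repeated measures ANOVA test was used for normally distributed data and Bonferroni test was used for post-hoc comparisons". The alternative is: "Friedman test was applied to non-normally distributed data and Dunn-Bonferroni test was used for post-hoc comparisons".

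The section gives no Shapiro-Wilk cut-off and no rule for the case where test and histogram disagree. It does not say whether the check applies to a variable, a treatment group, a time point, residuals or differences. It names no paired test for the treatment comparison.

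**The concern.** Two measurements on the same patient are usually positively correlated. A test that treats 30 PRP sides and 30 laser sides as independent samples overstates the standard error of their difference. It then rejects too rarely and wastes the gain that a split-mouth design is chosen for.

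The normality rule adds a second problem. For paired data, the distribution that matters is that of the PRP-minus-laser difference (or the residuals of a model), and the plan mentions neither. With 11 pain times and no stated unit, two analysts could follow the same text and report different tests. If the check is run at each time, some comparisons concern means and others ranks. If it is run once for the whole curve, as ANOVA or Friedman requires, the plan does not say how 11 times in two groups become one verdict.

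**Working it through.** The plan has no sample-size calculation, SD, correlation or effect size, so it has no figure to reproduce. From the documents: n = 30 pairs, 11 pain times, significance level 0.05 (taken as two-sided). Everything else below is assumed.

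**1. Cost of ignoring the pairing (normal approximation).** The unpaired test uses variance 2σ²/n for the mean difference. The true variance is 2σ²(1−ρ)/n, where ρ is the within-patient correlation. Let Φ be the standard normal distribution function and δ the difference in SD units.

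- Actual alpha = 2[1 − Φ(1.96/√(1−ρ))]
- Paired power = Φ(δ√n/√(2(1−ρ)) − 1.96)
- Unpaired power = Φ(δ√n/√(2(1−ρ)) − 1.96/√(1−ρ))

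For ρ = 0.3, 1.96/√0.7 = 2.343, so alpha = 0.019. With δ = 0.5, δ√n/√(2(1−ρ)) = 0.5 × 5.477/√1.4 = 2.315. Paired power is Φ(0.355) = 64% and unpaired power is Φ(−0.028) = 49%.

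| ρ | Actual alpha, unpaired | Power, paired | Power, unpaired |
|---|---|---|---|
| 0 | 0.050 | 49% | 49% |
| 0.3 | 0.019 | 64% | 49% |
| 0.5 | 0.006 | 78% | 49% |
| 0.7 | 0.0003 | 94% | 48% |

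Simulation of the rule as written, with an independent-samples t test and the check run at each time, agrees: type I error was 0.020 to 0.025 at ρ = 0.3 and 0.005 to 0.010 at ρ = 0.5. A fixed paired t test stayed at 0.042 to 0.055 in all scenarios, including ρ = 0.7. A separate run with VAS-like data, ρ of 0.3 to 0.5 and a 1-point difference gave 36% power for the written rule against 49% to 64% for the paired analysis.

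**2. If the check is run on raw scores at each pain time.** There are then 11 × 2 = 22 Shapiro-Wilk tests. With exactly normal, independent data, the chance of at least one false rejection is 1 − 0.95²² = 68%. The expected number of times sent to Mann-Whitney is 11 × (1 − 0.95²) = 1.1. The simulations used 30 pairs, 600 runs per scenario, serial correlation 0.7 and ρ of 0.3, 0.5 and 0.7. The floored patterns assumed a 0–10 scale, means falling from about 5 to 0.6, and SD 2.

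| Assumed data | Trials mixing t and Mann-Whitney | Times sent to Mann-Whitney, of 11 | Raw-score and difference verdicts disagree |
|---|---|---|---|
| Normal | 63–68% | 1.1 | 14% of times |
| Floored, continuous | 100% | 4.5–4.7 | 36–40% |
| Floored, integer | 99.8–100% | 6.9–7.1 | 39–53% |

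**3. Why raw scores are the wrong quantity for paired data.** With a skewed (exponential) patient effect shared by both sides and normal errors, the differences are exactly normal. In 10,000 samples of 30 pairs, raw scores failed Shapiro-Wilk in at least one group in 72%, and the differences failed in 4%.

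**4. Does pre-testing inflate alpha?** Choosing paired t or signed-rank by Shapiro-Wilk on the differences (n = 30, 10,000 runs each for normal, t with 3 df and Laplace data) gave 0.050 to 0.052. The two fixed tests gave 0.045 to 0.053. Pre-testing caused no material inflation.

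**The case against.** The plan refers only to the data and gives no unit for the check. If the check is made once per variable, pain gets one method and no mixture arises. Checking group distributions is also the natural companion of an independent-samples test, so the wrong-quantity complaint largely follows from the missing pairing; once the tests are paired, the same sentence could be read as a check of differences. Student t is not labelled as unpaired; only Mann-Whitney is unambiguously an independent-samples test.

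The simulated sizes depend on an assumed scale. With continuous scores away from the floor (means 6 to 3, SD 1.5, ρ = 0.4), about 1 of 11 times is called non-normal and the two verdicts disagree at 1.4 of 11, although a mixture still arises in 63% of trials. In that pattern, with a difference of 0.5, paired t and signed-rank disagree on significance at one or more times in 8% of trials. With floored integer scores and a difference of 0.5 to 1.0 point, the figure is 15% to 24%, but at most about 2.9% per time point. Such a disagreement is between two valid tests and is not in itself an error.

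These points stand, and they limit the claim. A reader might infer that the pain curve is certain to be tested with mixed methods, that raw scores were checked, that a histogram may overrule Shapiro-Wilk, or that the pre-test inflates false positives. The text states none of the first three, and step 4 contradicts the last. What survives is that no paired comparison is named, and that neither the unit of the check nor the route to one choice over time is defined.

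**Conclusion.** The concern holds, mainly as a pairing problem. The rank branch is explicitly unpaired and the t branch names no paired version. If both are unpaired, a nominal 0.05 test runs at roughly 0.01 to 0.02 for ρ of 0.3 to 0.5 (0.006 to 0.019 by formula). Power for a 0.5 SD difference falls from 64–78% to 49%. The error is conservative: it makes a real difference easier to miss and does not produce false positives. The loss vanishes at ρ = 0 and grows with ρ, which the documents do not give.

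The normality switch is a secondary fault. It leaves the method undefined and, if run on raw scores at each pain time, looks at the wrong distribution and makes a mixture of mean and rank comparisons likely (about 63% of trials with near-normal data, over 99% with an assumed floored 0–10 integer scale). Its harm is incoherence and discretion.

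**What to change.** Delete the normality switch for continuous outcomes. Name one analysis of the within-patient PRP-minus-laser difference and use it at every time point: a paired mean difference with its confidence interval. For VAS, a mixed model is an alternative, with patient, treatment, time, treatment-by-time and order of surgery, and with allowance for correlation among repeated scores on the same side. This model also replaces the ANOVA/Friedman choice. The same structure can serve edema and mouth opening with their 3 measurement times.

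Report the signed-rank test at all time points as a sensitivity analysis. Examine differences or residuals only as a diagnostic that cannot change the main test.

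The cost is a few sentences in the Statistical Analysis Plan section and no new data. That section is written in the past tense, so an analysis already done would have to be rerun and the change of method reported. One drawback is that late pain scores may include many zeros, where a mean-based result leans on n = 30; the signed-rank results address this. The change does not settle which of the 11 pain comparisons carries the conclusion, and it does not cover the categorical outcomes.
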